***Tertiary Outcome Measures:***

- 1) Patients ages 8 years of age and older and parents of patients ages 3–17 years of age will answer a general health question noted below:

**At time of discharge from the hospital:**

“Since you left the emergency department, how has your pain been? “No pain since in the Emergency Department, “Much better, “A little better, “The same, “A little worse, “Much worse

- 2) Oxygen saturation at discharge
  - Data being collected: Vital Signs
- 3) Medication Quantification Scale (MQS) pre-dose and on day of discharge; daily.
- 4) Other Patient Outcomes not listed as secondary outcomes

***Patient Reported Outcome (PRO) Data Collected:***

- 1) Pediatrics - Ages up to and including 17 years old

- **Pediatric PROMIS:** (35 items)

To be completed by patients ages 8–17 years of age and parents of children ages 5–17 years of age.

- (a) pain behavior (8 items),
- (b) pain interference (8 items),
- (c) pain intensity (1 item),
- (d) physical stress experiences (8 items), and
- (e) fatigue domains (10 items)

- **Peds QL SCD module:** (19 items)

To be completed by children ages 5–17 years of age and parents of children ages 3–17 years of age

- (a) Pain and Hurt (9 items) and
- (b) Pain Impact (10 items) domains

Total Pediatric PRO items to complete: 54 + 1 general health question = 55 items

- 2) Adults – 18 years of age and older

- (a) **PROMIS:**(25 items)

- (a) pain behavior (8 items),
- (b) pain interference (8 items),
- (c) pain intensity (1 item), and
- (d) fatigue (8 items)

(a) **PROMIS ASCQ-ME** (48 items)

- (a) Emotional Impact Short Form v2.0 (5 items),
- (b) Pain Episode Frequency and Severity (5 items),
- (c) Pain Impact Short Form v2.0 (5 items),
- (d) Sickle Cell Medical History Checklist (9 items),
- (e) Sleep Impact Short Form v2.0 (5 items),
- (f) Social Functioning Impact Short Form v2.0 (5 items), and
- (g) Stiffness Impact Short Form v2.0 (5 items)

Total adult PRO items to complete: 64 items + 1 general health item = 65 items

#### 4.5.1 Schedule of Events

The Schedule of Events (table 3) summarizes data collection for each time point in the study.

Table 3: Schedule of Events

	Screening	Pre-Dose 	Day 1 	Day 2 	Day 3-7 	Day 8 or Discharge 	Day 14 and/or Day 28 
I/E	X	X					
Demographics and Genotype		X					
Study Treatment Assignment		X					
Medical History	X	X					
Pain Crisis Start Date and time a		X					
Time of Last IV opioid/Pain Crisis End date and time b						X	
Number of ED visits/hospitalizations in last year (excluding current)		X					
ED admission information		X					
Time of IV placement		X					
Conmeds		X	X	X	X	X	
CMP d	X d	X d		X d			
BHCG e		X					
Research Labs		X		X		X	
Vital Signs f	X		X	X	X	X	
Pain Score f	X		X	X	X	X	
PROs (PROMIS/Peds) QL/ASCQ-Me (adults)		X (within 12 hours)					X
MQS Score		X	X	X	X	X	X
Symptoms Questionnaire g		X		X	X	X	X
Opioid Monitoring h	X	X	X	X	X	X	X
Maintenance Fluid Monitoring h		X	X	X	X	X	
AE i		X	X	X	X	X	X
SAE i		X	X	X	X	X	X
Study Drug Administration j			X	X	X	X	

Continued on next page...

Table 3 – *continued from previous page...*

---

- 1 – Predose is all information that is collected before the start of study drug.
- 2 – Day 1 is from the start of Study Drug to midnight of the day study drug is started. Pre-Dose and Day 1 may occur on the same day.
- 3 – Day 2 is the day after study drug is administered (starting at midnight of the day the study drug is started).
- 4 – Individual patient hospitalization duration will vary. Patients may be discharged at any time between Day 1 through Day 7.
- 5 – Day 8 is the day that the last dose #21 will be given for patients who have not yet been discharged.
- 6 – If patients are not discharged by Day 8, an AE/SAE review will occur daily until Day 14. ED revisits and hospital admissions will be captured through 28 days following hospital discharge.
- a – Pain Crisis start date/time is defined as the date/time the patient started experiencing pain (this could be before ED visit).
- b – Pain crisis end date/time is defined as the date/time of last dose of parenteral opioid delivery.
- c – Research labs: will be obtained with routine daily blood draws whenever possible and may be drawn on days when the research and clinical team suspect the patient may be discharged to avoid multiple venipunctures. In the event the patient is not discharged on that date, discharge labs should be drawn again prior to discharge. Baseline labs to be drawn before the start of study drug.
- d – Screening CMP from a clinically ordered CMP or the last CMP in the medical record within the last 12 months will be reviewed. If there are any values within higher than protocol defined cut offs for study drug withdrawal, then a CMP is to be drawn and reviewed prior to randomization. For participants with normal past CMP, a CMP will be done on day 2.
- e – Pregnancy test obtained at Pre-Dose for females 13 years and older.
- f – The first set of Vital Signs (including oxygen saturation) and Pain scores will be captured when the patient first presents to the Emergency Department. The highest and lowest pain scores will be recorded from Day 1 through Day 8 (or within 6 hours of Discharge). The first set of vitals signs after 6 am will be collected up until Day 8/Discharge, whichever comes first. Ensure oxygen saturation is captured at Pre-Dose and within 6 hours of Discharge.
- g – Symptoms Questionnaire will be completed daily through Day 14 or Discharge.
- h – Use of Parenteral Opioids will be documented every shift by nursing staff per standard protocol, including opioids delivered by the PCA device as well as any intravenous, intranasal and/or oral opioids used. Data on daily opioid use will be collected and recorded.
- i – AEs and SAEs will be monitored daily through discharge or through 14 days of hospitalization; Return ED visits and hospitalizations will be followed for 28 days after hospital discharge.
- j – Patients will be randomized within 12 hours of their initial dose of parenteral opioid in the ED or ward and Arginine will be administered TID.

## 4.6 Withdrawal from Study

As noted in Section [4.3.3 on page 27](#), this is a distinct concept from stopping the study intervention. Patients and/or guardians may decide to stop participating in the study at any time. If someone says they want to stop being in the study, they **USUALLY** mean they want to stop the intervention. Efforts should be made to clarify their specific preferences (withdrawal from the intervention, withdrawal from follow-up, withdrawal from data collection, etc.) Attempts should be made to continue safety data collection.

## 5 Data Analysis

All analyses will be undertaken by the intention-to-treat (ITT) principle. Patients who drop out (discontinue study drug) will be followed and included in the ITT analysis. All statistical tests of hypotheses will be two-sided.

The hypotheses of this study are:

1. Arginine therapy will decrease time-to-crisis resolution in children with an acute sickle cell vaso-occlusive pain episode compared to placebo.

2. Arginine therapy will lower total parenteral opioid use (mg/kg) compared to placebo.
3. Arginine therapy will improve pain scores compared to placebo.
4. Arginine will have similar safety profile than placebo.
5. Arginine therapy will improve global arginine bioavailability and mitochondrial activity.

## 5.1 Specific Aim Analyses

**Specific Aim 1: To determine the efficacy of IV L-arginine, when added to standard therapy, on the time-to-crisis resolution in children with SCD and VOE compared to placebo.**

The primary outcome (time-to-crisis resolution) will be analyzed by a Van Elteren test, stratified by clinical center and age group. The significance level for the primary comparison will be set at 0.05. The total length of stay in the hospital will also be analyzed, and this is expected to show the same result as the analysis of the primary outcome.

In addition to the assessment of the statistical significance of the treatment effect, the distribution of the primary outcome in each treatment arm using standard summary measures and an estimated difference in means between the two arms with a two-sided 95% confidence interval will be described.

The overall significance level for statistical tests on the secondary outcomes will be set at 0.05. Holms method will be used to adjust for multiple comparisons. The numeric secondary outcomes (opioid use, change in pain, and PRO measures) will be analyzed in the same manner as the primary outcome.

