Outcomes:	
Primary Outcome: time-to-crisis resolution
 
Secondary and Other Outcomes: Length of hospital stay, total parenteral opioid use, pain scores, Patient Reported Outcomes (PROs), oxygen saturation at discharge, rate of acute chest syndrome, ED or hospital readmission rates, requirement for blood transfusion, and pain medication MQS.

Study Population:	This study will enroll 360 patients in the United States that are 3–21 years old with an established diagnosis of sickle cell disease (any genotype) that are requiring medical care in an acute care setting (ED, hospital ward, day hospital, clinic) for pain not attributable to non-sickle cell causes.
Phase:	Phase 3
Description of Sites/Facilities Enrolling Participants:	
10 sites total (United States):
 
 
• Children’s Hospital Los Angeles
 
• Children’s Healthcare of Atlanta at Egleston
 
• Children’s Healthcare of Atlanta at Hughes Spalding
 
• Children’s Hospital of Philadelphia
 
• Children’s National Medical Center
 
• Medical College of Wisconsin/Wisconsin Children’s Hospital
 
• Nationwide Children’s Hospital
 
• Texas Children’s Hospital/Baylor College of Medicine
 
• UCSF Benioff Children’s Hospital
 
• Washington University/St. Louis Children’s Hospital
 

*Continued on next page...*

Table 1 – *continued from previous page...*

Description of Study Intervention:	Arginine is a safe nutritional supplement that is FDA approved in parenteral form for growth hormone stimulation testing, with nearly 50 years of safety experience through its common use by endocrinologists.  Route of administration: IV  Dose: Participants will be randomized to one of two study arms: 

• A one-time L-arginine loading dose (200 mg/kg IV) + standard dose (100 mg/kg IV TID); OR

• Placebo (normal saline) loading dose (2ml/kg IV) + 1ml/kg IV TID.

Study Duration:	6 years
Participant Duration:	28 days after discharge

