### 4.2 Randomization

Subjects will be randomized to receive either IV arginine or placebo. Permuted-blocks, stratified by clinical center and age group (<12 vs.  $\geq 12$ ), will be used. Equal allocation randomization tables will be provided by the Data Coordinating Center to the site research pharmacies. Randomization numbers will be delivered to the clinical center staff using a web-based system. This system will use each enrolled patient’s age group (<12 vs.  $\geq 12$ ) to deliver the next assigned treatment. Each site research pharmacy will use a randomization number to look up the treatment assignment and prepare the appropriate study drug. The randomization number will be recorded in the database.

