## 5.2 Sample Size Calculations and Statistical Power

Based on a previous small trial, the difference between arginine and placebo groups is approximately 0.7 days (length of stay, which parallels time to crisis resolution). A Type I error bound of 0.05 (alpha) for the primary hypothesis will be used and it will be assumed that age is not informative of outcome (a conservative bound for sample size). A simulation-based approach is used to determine the sample size required to detect a difference (shift in distribution) of 0.7 days with 85% power. In order to simulate placebo outcomes, time-to-crisis resolution data from the MAGiC trial (both arms combined, as the treatment effect did not reach statistical significance) was used. For the arginine arm, outcomes were simulated from the same distribution, shifted down by 0.7 days. 5,000 trials were simulated. This process resulted in a required sample size of 166 per arm. Accounting for withdrawal (~1%), interim efficacy monitoring (inflation of 2%), and crossover/non-adherence (3%, for example, arginine subjects who do not receive a sufficient amount of study drug) results in an overall inflation of about 8% or a total of 180 per arm. Prior to the first interim analysis (after approximately 100 subjects), the DCC and CCC principal investigators, along with the DSMB, will review, blinded to by-treatment results, summaries of the outcome distribution (mean, median, IQR with both arms combined – to compare with MAGiC data), withdrawal rate, and non-adherence rates and may adjust the target sample size accordingly, as funding allows.

Given a total sample size of 180 per arm, the effect size that will be detectable in subgroup analyses of the primary outcome, for example, a differential treatment effect based on gender or hydroxyurea use will also be reported. With 85% power, it will be possible to detect an effect size (difference in differences) of about 1.3 days, or approximately 1.9 times the main treatment effect size for which the study is powered. With 80% power, it will be possible to detect an effect size of 1.2, or 1.7 times the main treatment effect size.

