## 5.5 Interim Analyses

The Data and Safety Monitoring Board and trial monitoring plan are discussed in detail in the Data and Safety Monitoring Plan. A two formal interim efficacy analyses of accumulating data, after approximately 150 and 250 subjects are enrolled, to be reviewed by the DSMB is proposed. Aside from these formal analyses, the DSMB will meet at least yearly to review safety data.

Early stopping will be considered if efficacy has been established. Two-sided O'Brien-Fleming boundaries, implemented using a flexible alpha-spending approach, will be used for efficacy monitoring. Specifically, the significance levels that will be used at the first and second interim analyses are 0.001 and 0.014, respectively. If the trial reaches the anticipated total sample size, a significance level of 0.046 will be used for the final test.

As the trial can provide valuable scientific information, even in the face of a non-significant primary result, early stopping for futility is not anticipated. However, the DSMB and NHLBI will evaluate all aspects of the trial and determine at any point in time whether futility should be considered. It is expected that an informal, conditional power approach will be used to provide statistical information to guide the futility analysis if and when needed. Specifically, the probability of the study finding a significant effect, if continued, will be calculated under a range of plausible true effect sizes. A conditional power less than 20%, given the most liberal plausible effect size will indicate futility. The DCC biostatistician will point out assumptions, advantages, and limitations of the futility analysis approach to the DSMB. The DSMB will consider other factors, including the burden of finishing the trial at its current point, in its deliberations.

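### The primary test leaves unused baseline data that may predict crisis length; prespecified covariate adjustment could add power at very little cost

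*Combined protocol and SAP*

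**What the plan says.** Section 5.1, Specific Aim 1: "The primary outcome (time-to-crisis resolution) will be analyzed by a Van Elteren test, stratified by clinical center and age group". The strata are those of the randomization in Section 4.2: "Permuted-blocks, stratified by clinical center and age group", with age split at 12 years. The Synopsis lists "10 sites total (United States"), so there are up to 10 × 2 = 20 strata. Section 5.1 adds a difference in means with a 95% confidence interval and does not mention adjusting it. The numeric secondary outcomes follow the same method.

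Table 3 (Section 4.5.1) and its notes show that genotype, the start time of the pain crisis and the "Number of ED visits/hospitalizations in last year (excluding current") are collected before dosing, and that a first pain score is taken at presentation. None of these enters the primary test. Hydroxyurea use and sex appear only in the subgroup interaction models of Section 5.3. The sensitivity analyses in Section 5.4 concern missing data from withdrawals.

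Section 5.2 sizes the trial for a 0.7-day shift with 85% power. On age it says "it will be assumed that age is not informative of outcome (a conservative bound for sample size"). No other baseline variable is mentioned there.

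**The concern.** Children enter this trial at different points in a crisis. The outcome clock starts at study drug delivery (Section 4.5), but pain may have begun before the ED visit (Table 3, note a), and up to 12 hours may have passed since the first IV opioid dose (Section 1.6). Any genotype is eligible. It is therefore plausible that presenting severity, elapsed time, genotype and recent utilization explain some of the spread in remaining crisis time.

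If they do, a test that ignores them leaves that spread in the error term and has less power than it could have at the same sample size. The planned effect rests on length of stay in one small trial (Section 5.2), where Section 2.8 calls the reduction a trend. Any enlargement after the blinded review depends on funding, so power available from data already collected is worth having.

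**Working it through.** **Inputs from the documents.** A 0.7-day shift, 85% power, 166 per arm before inflation and 180 after (Section 5.2). Alpha: "A Type I error bound of 0.05 (alpha) for the primary hypothesis will be used"; tests are two-sided (Section 5). Allocation is 1:1: "Equal allocation randomization tables will be provided by the Data Coordinating Center to the site research pharmacies" (Section 4.2). Up to 20 strata.

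**Assumption.** R², the share of within-stratum outcome variance explained by the baseline covariates, is not given anywhere. A range of 0 to 0.30 is shown.

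**1. The plan's own figure.** The 166 per arm comes from 5,000 simulated trials on data from the MAGiC trial, whose spread and shape are not in the documents, so it cannot be reproduced independently. It can be used for calibration under the normal formula n = 2 SD² (1.960 + 1.036)² / 0.7²:

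SD = 0.7 × √(166/2) / 2.996 = 2.13 days.

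Two cross-checks agree with Section 5.2. The detectable interaction at 180 per arm is 2 × 2.13 × √(2/180) × 2.996 = 1.34 days, or 1.92 times 0.7 (stated: about 1.3 days and 1.9 times). The inflated size is 166 × 1.08 = 179.3, rounded up to 180.

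**2. Formula for the gain.** Adjustment replaces SD by SD × √(1 − R²). The SD cancels:

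power = Φ(2.996 / √(1 − R²) − 1.960), and n per arm for 85% power = 166 × (1 − R²).

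Example, R² = 0.10: 2.996 / 0.949 = 3.158; 3.158 − 1.960 = 1.198; power 88.5%; n = 149.4, so 150.

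**3. Simulation of the rank tests.** 332 children in 20 strata (14 of 16 and 6 of 18), equal arms within each stratum, 10,000 trials per cell. The outcome was either normal or lognormal, each scaled so that the Van Elteren test had about 85% power for the 0.7-day shift. One baseline score stands for the combined covariates, with a slope pooled over strata; for the lognormal outcome, R² refers to log time. The Monte Carlo standard error is √(0.85 × 0.15 / 10,000) = 0.4 points.

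| R² | Formula power | n per arm for 85% | Van Elteren (normal / lognormal) | Rank ANCOVA (normal / lognormal) |
|---|---|---|---|---|
| 0 | 85.0% | 166 | 85.5 / 84.5% | 85.4 / 84.4% |
| 0.05 | 86.7% | 158 | 85.1 / 84.9% | 86.3 / 86.2% |
| 0.10 | 88.5% | 150 | 84.9 / 85.2% | 87.9 / 87.8% |
| 0.20 | 91.8% | 133 | 84.8 / 84.3% | 90.6 / 89.8% |
| 0.30 | 94.8% | 117 | 85.2 / 84.8% | 93.4 / 92.5% |

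With no treatment effect, both tests rejected in 4.8% to 5.3% of trials. The simulated gain is about 1 point at R² = 0.05, 3 at 0.10, 5 to 6 at 0.20 and 8 at 0.30. The formula column is a large-sample ceiling that the rank test does not fully reach.

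**4. Cost if the covariates carry no information.** At R² = 0 the two tests are indistinguishable above. A smaller simulation (1,500 trials, lognormal with log-scale SD 0.6 and median 3.74 days, both assumed) gave 83.1% unadjusted and 82.5% adjusted. That 0.6-point difference is less than the standard error of one cell, √(0.83 × 0.17 / 1,500) = 1.0 point.

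**5. Final-look level.** Section 5.5 says "a significance level of 0.046 will be used for the final test". At 0.046 and 166 per arm, the formula gives 84.2%, 87.8% and 91.2% at R² of 0, 0.10 and 0.20, so the comparison hardly changes. The plan's 2% inflation for interim monitoring is meant to cover this.

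**The case against.** The strongest objection is that nothing in the documents shows these variables to be prognostic for this outcome. The nearest statements link low arginine to admission (Section 2.3) and to pain severity and need for hospitalization (Section 5.1, Aim 3). A reader might take the correlation of 0.86 in Section 2.8 as support, but it relates length of stay to total opioid use during the stay, which is measured after randomization and cannot serve as a covariate. This objection stands: the gain is conditional and may be zero.

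A reader might also infer that the plan treats age as uninformative, so that only center can reduce variance. The documents do not support this. The age assumption serves sample-size planning only, and age remains a stratum in the analysis.

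Nor is the trial shown to be underpowered or the test wrong. The test respects the randomization strata, the size is inflated from 166 to 180 per arm, and a blinded pooled review may change the target.

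There are practical objections too. Onset time may rest on recall. The first pain score is defined at ED presentation, although children may enter from a ward, day hospital or clinic. Excluding early responders may narrow the range of severity. Four covariates would sit on strata averaging 360 / 20 = 18 children. These points call for a short list and a missing-value rule, but they do not rule out adjustment: the slopes are pooled over all strata. Finally, a rank analysis of covariance changes the p-value and not the planned mean difference. That is correct, and the estimate needs its own adjustment.

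**Conclusion.** This is a missed efficiency and a cheap improvement, not an error. The Van Elteren test is valid and its 85% power does not rely on adjustment. On the simulated figures, adjustment would raise power from about 85% to between 86% and 93% for R² between 0.05 and 0.30, with under 1 point lost at R² = 0 and type I error near 5%.

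The result rests on an assumed R², a shift model, outcome shapes chosen for illustration, and complete covariates without interim looks. A stronger claim, that the trial is known to give up power or that adjustment is worth 11% or 25% more children, is not supported. Those percentages are 1/(1 − 0.10) and 1/(1 − 0.20): the large-sample ceiling at two assumed values of R².

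**What to change.** Before the first efficacy look at about 150 subjects, amend Section 5.1 as follows:

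- Make the primary test a stratified rank analysis of covariance that keeps the center by age-group strata.
- Fix a short covariate list: presentation pain score, prior-year ED visits and hospitalizations, genotype (SS or other), and time from pain onset to randomization.
- State a simple rule for missing covariate values, including the presentation pain score of children who enter outside the ED.
- Use the same test at both interim looks and at the final analysis.
- Report a covariate-adjusted mean difference with its 95% confidence interval.
- Keep the unadjusted Van Elteren test as a named sensitivity analysis.

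The blinded pooled review at about 100 subjects (Section 5.2) offers a chance to check, with arms combined, whether these covariates relate to the outcome before the list is fixed. If the sponsor prefers to leave the primary test unchanged, the minimum is to name the adjusted analysis as a prespecified supportive analysis.

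The cost is SAP wording and minor programming, with no new data. The downside is committing to the covariates in advance, and a negligible loss of power if they prove uninformative.

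### Section 5.1 names no strata for the mean difference and its 95% CI; read plainly, it is a two-sample interval, which is somewhat too wide after randomization stratified by center and age group

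*Combined protocol and SAP*

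**What the plan says.** Section 4.2 sets the randomization: "Permuted-blocks, stratified by clinical center and age group" (under 12 against 12 and over), with 1:1 allocation ("Equal allocation randomization tables will be provided by the Data Coordinating Center"). The synopsis (Section 1.1) lists ten sites, so there are up to 10 × 2 = 20 strata. Block size is not given.

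Section 5.1 carries the same factors into the tests. The primary outcome "will be analyzed by a Van Elteren test, stratified by clinical center and age group", and the Mantel-Haenszel tests under Aim 2 are stratified in the same way. For the size of the effect, the section promises summary measures by arm and "an estimated difference in means between the two arms with a two-sided 95% confidence interval will be described". That sentence names no strata, model or weights. The numeric secondary outcomes (opioid use, change in pain, PROs) "will be analyzed in the same manner as the primary outcome".

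No other section supplies the method. The linear model in Section 5.3 is for subgroup interactions and has no center term.

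**The concern.** Blocking within strata keeps the arms balanced in each center and age group. Differences between strata then largely cancel out of the treatment comparison. A two-sample standard error does not know this: it uses the whole within-arm variance, including the part that lies between strata, and so overstates the uncertainty.

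The Van Elteren test gives a p-value and no effect in hours. The mean difference and its interval are the only treatment-effect estimate that the plan names for the primary outcome. If the interval is wider than the design warrants, the headline effect looks less certain than it is. Some trials would then report a significant stratified test beside an interval that includes zero when they need not. The same applies to the numeric secondary outcomes if the shared manner of analysis extends to the interval.

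**Working it through.** **The plan's own figures.** The plan states no interval width, so there is none to reproduce. A scale can be taken from Section 5.2: 166 per arm, a 0.7-day shift, 85% power, two-sided 0.05. Inverting the normal two-sample formula gives

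SD = 0.7 × √(166/2) / (1.960 + 1.036) = 2.13 days.

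This is a back-calculated, normal-theory equivalent. The plan obtained 166 by simulation from the earlier magnesium trial's data and gives no SD. As a partial check, the same SD gives a detectable interaction of 4 × 2.13/√360 × (1.960 + 1.036) = 1.34 days at 85% power and 1.26 days at 80%, against the stated 1.3 and 1.2. The ratios below do not depend on the SD.

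**Formulas.** Let N = 360 with equal allocation, and let R² be the share of outcome variance between strata.

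- Two-sample half-width: 1.96 × 2 × SD/√N = 1.96 × 2 × 2.13/√360 = 0.440 day.
- Stratum-adjusted half-width: 0.440 × √(1 − R²).
- Width ratio: 1/√(1 − R²).
- Coverage of the two-sample interval: 2Φ(1.96/√(1 − R²)) − 1.
- Patients in a stratum-adjusted analysis of the same width: 360 × (1 − R²), that is 360 × R² fewer.

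| R² (assumed) | Adjusted half-width, days | Two-sample too wide by | Its coverage | Fewer patients for same width |
|---|---|---|---|---|
| 0 | 0.440 | 0% | 95.0% | 0 |
| 1% | 0.438 | 0.5% | 95.1% | 3.6 |
| 5% | 0.429 | 2.6% | 95.6% | 18 |
| 10% | 0.417 | 5.4% | 96.1% | 36 |
| 20% | 0.393 | 11.8% | 97.2% | 72 |

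**Simulation check.** There were 4,000 trials per R², each with 360 patients in 20 unequal strata, a gamma-skewed outcome and a true 0.7-day effect. Blocks of 4 were assumed. A two-sample t interval was compared with a linear model with stratum effects and a model-based standard error.

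| R² | Half-width, two-sample / adjusted | Two-sample wider by | Coverage, two-sample / adjusted | Interval excludes zero, two-sample / adjusted |
|---|---|---|---|---|
| 0 | 0.440 / 0.440 | −0.2% | 95.3% / 95.3% | 88.0% / 87.9% |
| 5% | 0.440 / 0.430 | 2.4% | 95.7% / 95.1% | 88.2% / 89.2% |
| 10% | 0.441 / 0.419 | 5.2% | 96.1% / 95.2% | 88.5% / 90.2% |
| 20% | 0.441 / 0.395 | 11.5% | 97.5% / 95.4% | 90.0% / 93.4% |

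The Monte Carlo standard error of a coverage figure is about √(0.95 × 0.05/4,000) = 0.3 percentage points. The simulation agrees with the formulas. It did not run the Van Elteren test, so it does not say how often test and interval would disagree.

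**The case against.** The strongest reply is that the plan never calls the interval unadjusted. A stratum-adjusted difference is also a difference in means, and the sentence is descriptive, placed beside summary measures. This stands as a limit on the claim. A reader might infer that the plan has decided to ignore the strata, but the text leaves the method open. The two-sample reading is only the plain one, because the plan says so wherever it means an analysis to be stratified.

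A reader might also infer that the primary result is compromised. The documents do not support that. The confirmatory test is stratified, so its p-value, type I error and power are untouched, and an unadjusted interval would err on the cautious side around an unbiased estimate.

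The size cannot be settled from the documents. The primary outcome ends at the last parenteral opioid dose (Section 4.5), a treatment decision that may vary by center. Section 5.2 treats age as uninformative, but only as a conservative sizing assumption. Against this, Section 7.4 says that care is standardized across sites, which may lower R². At R² of 1% or less the matter is of no practical weight, and at 5% the effect on coverage is barely visible in simulation.

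Finally, it would be too strong to say that the trial throws away precision. With complete blocks the point estimate already has it, and only the reported interval fails to show it. Strata average 360/20 = 18 patients, so some blocks will be incomplete and the cancellation is close rather than exact. Nor should the loss be read as 360/(1 − R²) − 360 = 19, 40 or 90 patients. That is the extra recruitment a two-sample interval would need to match the adjusted width, which is a different question.

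**Conclusion.** The point holds in conditional form and is minor. Center and age group are named for randomization and testing but not for the effect estimate. If the interval is the two-sample one that the wording suggests, it is about 3%, 5% or 12% too wide at R² of 5%, 10% or 20%, and not too wide at all at R² = 0. These R² values are assumptions. The widths in days also rest on the back-calculated SD of 2.13 days.

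The cost is a wider reported interval and some avoidable cases of a significant test beside an interval that includes zero. Adjustment would not remove every such case, because the test compares ranks and the estimate compares means. Extending the point to the secondary outcomes assumes that the shared manner of analysis includes the interval, which the text suggests but does not spell out.

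**What to change.** Add one sentence to Section 5.1. It should say that the mean difference and 95% CI for the primary outcome, and for the numeric secondary outcomes analyzed in the same manner, come from a linear model with treatment and the randomization factors (center and age group), with a robust standard error. It should add that main effects of center and age group are used where center-by-age strata are very small. A stratum-weighted difference would serve the same purpose; what matters is to fix the method before unblinding.

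No new data are needed. Full strata use at most 20 − 1 = 19 further degrees of freedom out of 360, and main effects use 9 + 1 = 10. In the simulation at R² = 0, where adjustment cannot help, it widened the interval by only 0.2%. The primary test and the sample size do not change.
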